**ClinicalTrials.gov ID number:**

**NCT02750202**

**Approved by:**

**The Research Ethics Committee**

**Faculty of Health Sciences**

**University of Pretoria**

**Ethics Reference Number: 21/2016**

**Author:**

**[name]**

**Document Version: 24 Feb 2016**

## 1. INTRODUCTION

The global burden of HPV disease as represented in genital warts is very high, which in turn leads to high costs of healthcare and loss in quality of life [1-4]. The prevalence of HPV in Sub Saharan Africa is among the highest in the world [5-7]. In South Africa, extensive genital warts are not an infrequent finding in general gynaecology and oncology clinics, but accurate prevalence data are unavailable. Recently the occurrence of these lesions increased as HIV-related immune-compromise became more frequent [8,9]. Large, extensive or recurrent genital warts are more frequent in women with HIV related immunodeficiency and therefore this population provides unique opportunity to study changed viral epidemiology, immunity related research questions and novel treatment approaches.

The HIV epidemic causes large numbers of women to have a poor immunity, which makes them susceptible to opportunistic disease or more extensive viral disease. The HIV epidemic may also change the epidemiology of HPV viral disease as shown in cervical HPV related disease, causing changes in HPV type distribution and in the prevalence of HPV in the general population.

The financial and psycho-social burden of genital warts is well described and widely accepted in the developed world. Medical and destructive therapy for warts is generally very effective [10-13]. The unique problems posed by large or extensive genital warts are, however, not so easily solved and treatment of affected individuals remain very challenging.

Management options for these lesions currently include mostly surgery and cauterization because the lesions and affected area is too large for conservative medical treatment. Surgery often has disfiguring results and recurrence remains very frequent with all treatment modalities.

Recent data suggests that one of the reasons for recurrent or huge papilloma virus induced warts is the absence of antibody response in selected individuals [8,14,15]. In addition, data from recurrent respiratory papilloma cases suggest that vaccination with preventative quadrivalent vaccine can be therapeutic in many of these patients [16-18].

It is anticipated that the additional stimulation from a vaccine against the common wart-inducing HPV types (6 and 11) can help increase the production of protective antibodies in these susceptible women and can contribute to control the disease. In this prospective randomized trial, women with extensive genital warts will be studied, comparing those who have received quadrivalent HPV vaccine to a control group of women who have received hepatitis B vaccine.

## 2. HYPOTHESIS AND AIMS

The **main hypothesis** is that HPV preventative vaccine can play a role in the control of non-neoplastic HPV disease in women with and without HIV infection through the high antibody response elicited. In addition, it is the hypotheses of this study that:

- HPV types in genital warts are affected by vaccination with HPV4

- In a population with a high prevalence of HIV, the HPV type distribution differs from the published data
- HPV vaccines will have an effect on cervical HPV types and disease status
- The size or recurrence rate of extensive genital warts can be reduced by vaccination with HPV4 after surgical treatment

### **3. METHODS**

This will be a multi-centric study done at two different sites in South Africa, e.g. Pretoria Academic Hospitals, Stellenbosch University Hospital.

#### Patient selection:

Female patients referred or presenting with genital warts at each site will be eligible and evaluated against the inclusion and exclusion criteria.

Women who are clinically or severely immune-compromised will not be included into the study, but both HIV negative and HIV infected women will be included. Fifty women with large or recurrent genital warts will be recruited for this study from 2 sites in South Africa.

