#### Inclusion criteria:

- Female patient > 16 years
- Presence of problematic vulvo vaginal genital warts:
  - Largest tumour diameter > 3 cm
  - OR      Tumour on labia minora and labia majora OR bilateral > 1 cm each side
  - OR      Tumour in vagina/cervix as well as on vulva > 1 cm lesion each
- HIV negative
- HIV infected:
  - CD4  $\geq 300 \times 10^6$  cells/l
  - OR      viral load controlled
  - OR      ARV compliant > 6 months

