#### Exclusion criteria:

- Pregnant or planned pregnancy within 6 months
- Not able to comprehend study method or not able to attend all study visits
- Previous HPV vaccination
- Active known opportunistic infection or malignancy including PCP, PTB, oesophageal Candida or Kaposi sarcoma or lymphoma
- Known allergy to vaccines or content of vaccine
- Previous radiation for genital warts

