#### Recruitment:

Women with genital warts will be evaluated for inclusion into the study. Those who fit the inclusion criteria and are without any of the exclusion criteria will be fully informed and invited to participate.

The first target will be to recruit the first fifty consecutive eligible patients who have signed written consent; recruitment for the study will be done for at least 24 months.

First clinical visit:

- Evaluation genital lesions:  
On study entry tumour size and position will be documented graphically (see Appendix B diagram) and photographically and viral typing from the vulva wart and cervix will be done using Roche LA test.
- Evaluation immune status:  
HIV status and CD4/CD8 count will be recorded and tested and the serum will be collected for antibody testing. Cervical disease of clinical significance will be excluded or treatment offered if relevant.
- Randomization:  
Patients will be randomized to receive either HPV4 or Hepatitis B vaccine.
- Vaccination:  
The participants assigned to the test group will be administered HPV4 vaccine in three doses as recommended by the manufacturer. Participants assigned to the control group will receive Hepatitis B vaccine in three doses as recommended by the manufacturer.

Follow-up clinical visits: week 8, week 16 and week 24:

- Evaluation genital lesions:  
Three follow up visits will be scheduled two months apart at which time the lesion size will be recorded.
- Evaluation immune status:  
After month 6 or the third visit, the serum will again be collected for antibody level testing.
- Treatment decision:  
According to the clinical response as measured at month six and onwards, locally destructive or surgical treatment will be allowed according to the preference of the clinician and as determined by clinical factors.

Follow up after treatment:

- Follow up will be done at six monthly intervals.
- Evaluation genital lesions:  
At these visits lesion size will be determined and documented. HPV typing on the cervical and vulval lesions will be repeated at least once.
- Further treatment of warts:  
If needed, repeat surgery and/or local destruction will be allowed and documented. These will be around week 48 and week 72, or study exit.

Study exit:

- Participants will exit the study in week 72.

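### Do the HIV entry criteria let in women whom the protocol says it will bar, and could randomisation come before the eligibility results?

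*Protocol*

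**What the plan says.** All the relevant text is in the Protocol, section 3 (Methods).

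- **Patient selection** says women will be evaluated against the inclusion and exclusion criteria. It adds that "Women who are clinically or severely immune-compromised will not be included into the study", while both HIV-negative and HIV-infected women may enter. Neither clinical nor severe immune compromise is defined.
- **Inclusion criteria** accept an HIV-infected woman with a CD4 count of at least 300 × 10^6 cells/l, or "viral load controlled", or "ARV compliant > 6 months". The three are joined by OR.
- **Exclusion criteria** remove "Active known opportunistic infection or malignancy including PCP, PTB, oesophageal Candida or Kaposi sarcoma or lymphoma". They contain no CD4 level.
- **Recruitment** says "Those who fit the inclusion criteria and are without any of the exclusion criteria will be fully informed and invited to participate" and sets the target as the first fifty consecutive eligible, consented patients. Under the first clinical visit it lists, in order, evaluation of the lesions, evaluation of immune status ("HIV status and CD4/CD8 count will be recorded and tested and the serum will be collected for antibody testing"), randomisation ("Patients will be randomized to receive either HPV4 or Hepatitis B vaccine") and vaccination.
- The opening of Methods says "This will be a multi-centric study done at two different sites in South Africa".

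**The concern.** Two things look wrong on a first reading.

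First, the narrative bars severely immune-compromised women, but the lists admit an HIV-infected woman on viral-load control alone or on treatment compliance alone, whatever her CD4 count. The exclusions reach only infections and malignancies that are active and known. One of the two sites might apply the narrative sentence as an extra exclusion while the other works from the lists only, so the sites could enrol different women under one protocol. Section 4 plans to compare immune status and HIV status with the disease outcomes, so entry at the low end of immune status bears on a planned analysis.

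Second, testing, randomisation and vaccination share one visit, and no sentence makes randomisation wait for a result. Viral load is a qualifying condition but is not among the first-visit tests. If a woman of unknown status turned out to meet none of the three conditions after she had been randomised and vaccinated, the site would have to decide what to do with her in a trial of only fifty.

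A smaller mismatch sits beside these: Patient selection mentions recurrent warts, and the Inclusion criteria have no recurrence item.

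**Working it through.** No sample size, power or error rate is at issue. The check is a count of what the OR rule admits, followed by a reading of the order of steps.

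**1. What the OR rule admits.** The inputs are the three conditions in the Inclusion criteria: A = CD4 at or above 300, B = viral load controlled, C = compliant with antiretrovirals for more than 6 months. A woman is admitted if A or B or C holds. There are 2^3 = 8 profiles.

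| A | B | C | Result |
|---|---|---|---|
| yes | yes | yes | admitted |
| yes | yes | no | admitted |
| yes | no | yes | admitted |
| yes | no | no | admitted |
| no | yes | yes | admitted |
| no | yes | no | admitted |
| no | no | yes | admitted |
| no | no | no | refused |

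The rule admits 7 of 8 profiles. Of the 4 with CD4 below 300 it admits 3, one of them with viral load uncontrolled (C only). The observation about the missing CD4 floor is therefore correct.

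**2. Whether this contradicts the narrative.** A contradiction needs a woman whom one passage must admit and the other must refuse. There are two readings of the Patient selection sentence.

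- *As a summary of the lists.* The exclusion of opportunistic infection and malignancy covers the clinical part. The HIV conditions cover the severe part by refusing a woman who meets none of them. Nothing conflicts.
- *As a further restriction.* It refuses some women whom the lists alone would admit. A woman must then pass both tests, which is again consistent.

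A conflict appears only if severe immune compromise means a low CD4 count regardless of viral load or treatment. The Protocol does not say that. Which marker should govern is a clinical judgement for the investigators.

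**3. Order of steps.** HIV status, with a qualifying condition for an infected woman, is itself an inclusion criterion. The Recruitment text invites only women who fit the criteria and counts only eligible patients towards the fifty. A woman of unknown status has not been shown to fit. Within the first visit, immune evaluation is listed before randomisation, and its wording covers recording a known result as well as taking a new test. Compliance over more than 6 months can only come from history, and viral load can come from clinic records.

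**4. Consequence for the analysis.** Suppose a woman were still randomised in error. She would be 1/50 = 2% of the sample, as with any enrolment error in this trial. Her HIV status, CD4 count, viral load and treatment history at entry all predate allocation, so they cannot depend on the arm she drew. Keeping her in her assigned arm introduces no bias between arms. The same reasoning covers a site that admits more women with low CD4 counts: it changes who is studied, not the fairness of the comparison. HIV status and CD4/CD8 are recorded at entry, so the Section 4 comparison can be made and the immune range of the sample described.

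**The case for a change.** The strongest case for a change is that eligibility belongs in the protocol and cannot be left to a later analysis plan. If the narrative sentence is an extra exclusion, its terms are undefined and it appears in neither list, so a site working only from the lists would never apply it. The trial's hypothesis works through antibody response in women with and without HIV, so the immune range of those enrolled matters to the result. The only HIV and CD4 testing scheduled at entry sits in the same visit as vaccination, and the remedy would cost little: some wording, one data-sheet item and, for some women, a short return visit.

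Part of this stands. The phrase is undefined, the lists do not carry every possible meaning of it, and no sentence requires results on file or names the source of viral-load and treatment records. The first-visit list also does not ask which condition a woman qualified on. The mismatch over recurrent warts is real but is minor wording and has nothing to do with immune status.

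The step from there to a defect does not stand. That the two sites would read the text differently is conjecture. Randomising a woman before her eligibility is known would go against the Recruitment text. The remedy would have to leave the clinical content to the investigators, so it amounts to aligning words and writing down a step that a screening form already performs.

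**Conclusion.** No change to the plan follows. The narrative sentence is looser than the lists, but the two are compatible on either reading. The missing results-on-file sentence is an operational detail that sites working from the Recruitment text would supply themselves. The 7 of 8 and 3 of 4 figures count combinations of conditions. The document gives no share of women in any of them, so no affected number can be derived, and each hypothetical error would be 2% of the sample.

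This rests on three assumptions: sites establish eligibility before allocating, as the Recruitment text implies; any woman randomised in error is analysed in her assigned arm; and HIV status and CD4/CD8 are recorded at entry as scheduled. Under these, the randomised comparison and the planned comparison with immune status are both sound. How the narrative sentence and the lists relate is for the investigators to reconcile in wording if they wish; no threshold or clinical rule is suggested here.

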#### Inclusion criteria:

- Female patient > 16 years
- Presence of problematic vulvo vaginal genital warts:
  - Largest tumour diameter > 3 cm
  - OR      Tumour on labia minora and labia majora OR bilateral > 1 cm each side
  - OR      Tumour in vagina/cervix as well as on vulva > 1 cm lesion each
- HIV negative
- HIV infected:
  - CD4  $\geq 300 \times 10^6$  cells/l
  - OR      viral load controlled
  - OR      ARV compliant > 6 months

#### Exclusion criteria:

- Pregnant or planned pregnancy within 6 months
- Not able to comprehend study method or not able to attend all study visits
- Previous HPV vaccination
- Active known opportunistic infection or malignancy including PCP, PTB, oesophageal Candida or Kaposi sarcoma or lymphoma
- Known allergy to vaccines or content of vaccine
- Previous radiation for genital warts

#### Recruitment:

Women with genital warts will be evaluated for inclusion into the study. Those who fit the inclusion criteria and are without any of the exclusion criteria will be fully informed and invited to participate.

The first target will be to recruit the first fifty consecutive eligible patients who have signed written consent; recruitment for the study will be done for at least 24 months.

First clinical visit:

- Evaluation genital lesions:  
On study entry tumour size and position will be documented graphically (see Appendix B diagram) and photographically and viral typing from the vulva wart and cervix will be done using Roche LA test.
- Evaluation immune status:  
HIV status and CD4/CD8 count will be recorded and tested and the serum will be collected for antibody testing. Cervical disease of clinical significance will be excluded or treatment offered if relevant.
- Randomization:  
Patients will be randomized to receive either HPV4 or Hepatitis B vaccine.
- Vaccination:  
The participants assigned to the test group will be administered HPV4 vaccine in three doses as recommended by the manufacturer. Participants assigned to the control group will receive Hepatitis B vaccine in three doses as recommended by the manufacturer.

Follow-up clinical visits: week 8, week 16 and week 24:

- Evaluation genital lesions:  
Three follow up visits will be scheduled two months apart at which time the lesion size will be recorded.
- Evaluation immune status:  
After month 6 or the third visit, the serum will again be collected for antibody level testing.
- Treatment decision:  
According to the clinical response as measured at month six and onwards, locally destructive or surgical treatment will be allowed according to the preference of the clinician and as determined by clinical factors.

Follow up after treatment:

- Follow up will be done at six monthly intervals.
- Evaluation genital lesions:  
At these visits lesion size will be determined and documented. HPV typing on the cervical and vulval lesions will be repeated at least once.
- Further treatment of warts:  
If needed, repeat surgery and/or local destruction will be allowed and documented. These will be around week 48 and week 72, or study exit.

Study exit:

- Participants will exit the study in week 72.

- In the absence of harm as determined at interim analysis or suggested by participant disease history, researchers will be unblinded for participant status at study exit and alternative vaccines will be offered to each of these women.

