#### Outcome measures:

Outcome measures will be: change in size of lesions before and after vaccination; incidence, time and size of recurrent disease; change in HPV type specific antibody titres before and after vaccination; change in prevalence of vaccine types HPV DNA on the cervix before and after vaccination; and change in prevalence of vaccine types HPV DNA in the warts after vaccination.

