#### **4. DATA COLLECTION AND HANDLING**

Data will be collected prospectively as described above. Hand drawings of the affected areas will be made at each visit (see Appendix B diagram). In addition, a standardised photograph will be taken of the vulvo-vaginal area for future comparison. The lesion diameters will be measured and noted. Data sheets will be used to collect all clinical and laboratory results. Data entry into a designed data base will be done from 12 months onwards until all patients have completed a follow up period.

Analysis will be done of the pre-and post-vaccination antibody levels, immune status and HIV status and comparison of the above measures with the HPV and HPV-associated disease outcomes will be made.

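### The study-exit rule, as naturally read, lets staff who recruit, measure and treat be unblinded woman by woman while the trial is still running; they should stay blinded until the last visit and database lock

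*Protocol*

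**What the plan says.** The rule stands in Protocol section 3 (Methods), under Study exit. It opens with a condition, "In the absence of harm as determined at interim analysis or suggested by participant disease history", and then states that "researchers will be unblinded for participant status at study exit and alternative vaccines will be offered to each of these women".

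Three other statements in section 3 fix its timing:

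- The bullet just before it reads "Participants will exit the study in week 72".
- Under Follow up after treatment, the late visits are described thus: "These will be around week 48 and week 72, or study exit". Study exit is listed there among a woman's own visits.
- Under Recruitment, fifty consecutive eligible women are sought, and "recruitment for the study will be done for at least 24 months".

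From month six, "locally destructive or surgical treatment will be allowed according to the preference of the clinician and as determined by clinical factors". The outcome measures begin with "change in size of lesions before and after vaccination; incidence, time and size of recurrent disease". Section 4 (Data collection and handling) has lesions drawn by hand and their diameters measured, and adds that "a standardised photograph will be taken of the vulvo-vaginal area for future comparison".

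The rule does not say which researchers are meant. It does not make unblinding wait for the last participant.

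**The concern.** Entry is consecutive, so week 72 arrives at a different calendar date for each woman. If codes are broken one woman at a time, the same team could learn the arms of those who have finished while it still enrols, measures and treats others.

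One woman's arm does not disclose another's. But staff would see outcomes by arm accumulate. If they come to believe that one arm does better, and can guess or predict which arm a masked woman is in, that belief can affect how a lesion is drawn or measured and whether it is treated or re-treated. Guessing might rest on the woman's response. Prediction would depend on the randomisation method, which this document does not give.

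Of the five outcomes, lesion size and recurrence are exposed. Treatment choice feeds into both, because surgery or local destruction changes the lesions measured afterwards. The antibody outcome and the two HPV DNA outcomes are laboratory measures and less exposed.

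**Working it through.** The protocol gives no figure for this overlap, so there is none to reproduce. The check is a calendar calculation.

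**Inputs from the protocol.** Fifty women (Patient selection); recruitment of at least 24 months (Recruitment); visits after entry at weeks 8, 16, 24, 48 and 72, which makes 50 × 5 = 250; exit at week 72.

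**Assumptions.** Even accrual over A weeks (24 months taken as 104 weeks); no dropout; unblinding at each woman's own exit; the no-harm condition already met by the first exit, unless an interim week T is given.

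**Formulas.** Woman *i* enters at t_i = (i − 0.5) × A/50. Her code is broken at max(t_i + 72, T).

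**Step 1: first code break against close of recruitment.** 72 weeks ÷ (365.25/12/7 weeks per month) = 16.6 months after entry, which is less than 24. With A = 104:

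- first entry at week 0.5 × 2.08 = 1.04, so first exit at week 73.0;
- last entry at week 49.5 × 2.08 = 102.96, so last week-72 visit at week 175.0;
- gap of 49 × 2.08 = 101.9 weeks.

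**Step 2: women unblinded when recruitment closes.** 50 × (A − 72)/A gives 50 × 32/104 = 15.4, or about 15. For 12 months (A = 52) it is 0. For 36 months (A = 156) it is 26.9.

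**Step 3: visits still to come, across all women, after a given point.** Ten women is an illustrative threshold; five and twenty are shown beside it.

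| Accrual | Point in time | Visits remaining (weeks 8+16+24+48+72) | Share of 250 |
|---|---|---|---|
| 24 months | five women unblinded, week 81.4 | 15+19+22+34+45 = 135 | 54% |
| 24 months | ten women unblinded, week 91.8 | 10+14+17+29+40 = 110 | 44% |
| 24 months | twenty women unblinded, week 112.6 | 0+4+7+19+30 = 60 | 24% |
| 12 months | ten women unblinded, week 81.9 | 0+0+0+17+40 = 57 | 23% |
| 36 months | ten women unblinded, week 101.6 | 20+23+25+33+40 = 141 | 56% |
| 24 months | no code broken before an interim at T = 104 (15 women unblinded then) | 4+8+12+23+35 = 82 | 33% |
| 24 months | no code broken before an interim at T = 128 (27 women unblinded then) | 0+0+0+12+23 = 35 | 14% |
| 24 months | T at or after week 175 | 0 | 0% |

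**Step 4: visits after the woman's own code break.** Her last visit is at t_i + 72 and her code is broken no earlier than that. The count is therefore 0 of 250 in every row. Step 3 measures calendar overlap: visits by women whose own arm is still masked, at a time when the arms of others may be known.

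**Step 5: the other reading.** If study exit means the end of the whole trial, no visit remains when codes are broken and the overlap is 0.

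**The case against.** The strongest objection is that no assessment is made with the woman's own arm known. A reader might infer from 110 of 250 that 44% of visits are compromised. The protocol does not support that, as Step 4 shows. For differential bias, staff must also guess or predict the arm of a masked woman; a change in habits that touches both arms alike does not bias the comparison. This stands, and it reduces the point to an indirect risk.

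The risk is also conditional. Study exit might mean the end of the trial. The interim analysis is undated and may come late. *Researchers* might exclude assessors and treating clinicians. Each of these would shrink or remove the overlap. But the text as written ensures none of them, and its use of study exit among a woman's own visits favours the per-woman reading.

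A reader might also infer that records are open to alteration, because section 4 lets data entry run until all women have completed follow-up, so an exited woman's sheets could be entered after her arm is known. This is minor. The measurements, drawings and photographs are made at the visits, before her code is broken, and later entry is transcription. The photographs would also allow lesion size to be re-read blind. They would not undo treatment choices made by staff who had seen results by arm.

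**Conclusion.** The point holds as a conduct rule that is badly fixed, not as a demonstrated bias. On its natural reading the rule allows codes to be broken from about 16.6 months after the first entry, while recruitment runs for at least 24. With even accrual over 24 months and the no-harm condition met in time, about 15 women would be unblinded when recruitment closes, and about 102 weeks would separate the first code break from the last week-72 visit. The overlap is smaller with a late interim and nil on the trial-wide reading.

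The exposed outcomes are lesion size and recurrence, together with treatment decisions. The size of any bias cannot be derived from the document. The rule should be amended because blinding lost during follow-up cannot be restored. Confidence is medium, since the wording admits a second reading.

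**What to change.** Amend the Study exit rule in Protocol section 3 in two respects:

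1. Staff who recruit, assess, treat or enter outcomes stay blinded until the last woman's week-72 visit is complete and the database is locked.
2. State whether study exit means the woman's own exit or the end of the whole trial.

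Leave the timing and condition of the alternative-vaccine offer as the protocol sets them, and have the offer handled by whoever holds the allocation code, outside the assessing team. The protocol names no such person. This assumes that the existing blinding already requires one; if not, the role has to be assigned.

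Under that assumption the cost is a change of wording. The drawback is that the clinical team learns each woman's arm later, and some staff may still learn it informally through the vaccine offer.
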